### **The definitions of DLT include:**

- Grade-4 nonhematologic toxicities;
- Grade $\geq$ 3 febrile neutropenia;
- Any grade-3 non-hematologic toxicities lasting more than 3 days despite of optimal supportive care;
- Grade-3 nonhematologic laboratory abnormalities that persist more than one week and require medical intervention or hospitalization;
- Grade-4 thrombocytopenia requiring platelet transfusion or leading to life-threatening bleeding event.
- Grade-4 neutropenia  $>$  7 days.

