## **6. ASSESSMENT OF SAFETY AND MANAGEMENT OF TOXICITIES**

### **6.1. Dose limiting toxicities (DLTs)**

DLTs are side effects of a drug or other treatment that are serious enough to prevent an increase in dose or level of that treatment in a clinical study. We use Common Toxicity Criteria for Adverse Events (CTCAE) 4.0 for grading of toxicities in this study.

The definition of DLTs in this study is the toxicities during the first cycle of treatment:

A DLT will be considered to be IP-related unless there is a clear, well-documented, alternative explanation for the toxicity. Delayed DLTs are adverse events that meet the criteria of DLTs that occur after the first cycle of treatment. Delayed DLTs need to be evaluated on a case-by-case basis to make sure that there is no cumulative damage to vital organ function.

Delayed DLTs will also be considered to estimate the MTD for HLX06 in this study.

All adverse events that meet DLT or delayed DLT criteria, as well as any Grade 3 or 4 infusion reactions no matter whether the event is a DLT must be reported to the Sponsor or its designee, within 24 hours.

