- **Grade  $\geq 3$  symptoms:** It is severe reaction, and recurs, or does not rapidly respond to symptomatic treatment and interruption of infusion, stop the infusion of IP immediately. Consider 0.2 to 1 mg of 1:10,000 solution of epinephrine for subcutaneous administration. Diphenhydramine 30-50 mg intravenous with methylprednisolone 100 mg (or equivalent) intravenously, as needed. Hospitalization might be needed for possible clinical sequelae.

**Hypertension:** Hypertension is among the most common toxicities of anti-angiogenic therapy. The incidence of hypertension could reach 20% by a single anti-angiogenic agent. Initiation of antihypertensive medications should be considered when BP is  $>140/90$ mmHg or if there is an increase in DBP  $\geq 20$ mmHg. If SBP  $>160$ mmHg, DBP  $>100$ mmHg, hypertensive crisis or if antihypertensive interventions do not provide appropriate BP control, the dose level of HLX06 should be decreased or held until antihypertensive therapy is effectively titrated. Although appropriate BP control is essential, excessive lowering of BP may also have detrimental cardiovascular consequences; careful selection of doses and close BP monitoring are crucial to avoid episodes of hypotension. Multiple antihypertensive drugs are being used to treat anti-angiogenic therapy-induced hypertension including calcium channel blockers, inhibitors of the renin-angiotensin system, beta-blockers and diuretics. At this time, however, no clinical evidence favoring one antihypertensive agent over another is available [19].

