**Severe proteinuria:** This is another common side effects observed in anti-angiogenic therapy. Severe proteinuria including nephritic syndrome may cause significant morbidity with a possible consequence of renal failure and fatality. It is recommended to suspend anti-angiogenic therapy at least temporarily for proteinuria  $\geq 2$  g/24 hours and to discontinue the therapy for nephrotic syndrome. The risks of severe proteinuria include higher dose of therapy, concurrent use of chemotherapy and renal cell carcinoma.[21] There are no evidence-based guidances for the management of anti-angiogenic therapy-induced proteinuria. If proteinuria is  $\geq 2$  g/24 hours during HLX06 therapy, stop the therapy, and the patients might resume the therapy after proteinuria decreases to  $<2$  g/ 24 hours at the next lower dose level, if the benefit of HLX06 is deemed to outweigh the risks, as judged by the Investigator.

**Bleeding:** This is a frequent complication of anti-angiogenic therapy. Two meta-analyses have found that the use of bevacizumab in combination with chemotherapy for the treatment of various tumor types conferred an increased risk of severe and fatal bleeding events and treatment-related mortality versus chemotherapy alone. Most cases involve low-grade mucocutaneous bleeding that can be managed by local treatment and usually does not interrupt

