#### **7.2.3. Procedures for subsequent infusions in a cycle**

Following the first infusion in a cycle, patients may receive additional infusions on day 8, 15 and 22 to complete the cycle of treatment. The maximum duration of IP to be administered to an individual patient in this study is one year.

The evaluations performed for the second to fourth infusion in a cycle are as follows:

1. Vital sign measurements to include temperature, pulse, and blood pressure will be obtained as defined in the Section 14.
2. Weight
3. Elective physical examination (including measurement of vital signs as well as pulmonary, heart, abdomen, and skin assessments)

---

 Detailed pharmacokinetic studies are conducted in the first week in Cycle 1 only.

 The samples are collected before and after one hour of first infusion in Cycle 1. Please refer to Section 9 for detailed time points.

4. ECOG performance status
5. Clinical laboratory tests (local and central laboratories) (Note: Lab data must be performed and reviewed before dosing)
6. Complete blood count (CBC) with differentials and D-dimer
7. Blood chemistry profile: fasting glucose, BUN, creatinine, alkaline phosphatase, ALT, AST, total bilirubin, total protein, albumin, globulin, sodium, potassium, chloride, calcium, magnesium, phosphorus, uric acid, lactate dehydrogenase.
8. Urinalysis.
9. Serum sampling for pharmacokinetic studies (*for first cycle only*)
10. Infusion of IP
11. AE assessment

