##### **7.2.4.2. Dose modification for subsequent infusions**

This study allows dose adjustment for toxicities. Dose modification is based on the toxicities from previous infusions. Patients who experience reversible DLTs **are** allowed to receive

---

 Any new Grade $\geq$ 3 laboratory abnormality, such as liver function test elevations, electrolyte fluctuation, or hematologic deterioration should be assessed for potential risk to continued dosing. In the event of uncertainty, the Medical Monitor should be contacted.

additional infusions at the next lower dose level, provided that the toxicities have reverted to grade≤1 in 28 days after last infusion, and that the patients still meet the inclusion criteria for adequate organ functions. Dose modification for reasons other than toxicities is not allowed, unless it is scientifically justifiable and must be agreed by the Sponsor.

*For patients who experience DLTs, re-escalation to the dose level causing DLT is not permitted.  
Up to two dose-level reductions per patient are allowed in this study.*

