#### **7.2.5. Discontinuation of patients from treatment**

Each patient has the right to withdraw from the study any time. Patients MUST discontinue Investigational Product (and non-investigational product at the discretion of the Investigator) for any of the following reasons:

- Withdrawal of informed consent (patient's decision to withdraw for any reason)
- Any clinical adverse event (AE), laboratory abnormality or inter-current illness, which, in the opinion of the investigator, indicates that continued participation in the study is not in the best interest of the patient.
- Pregnancy or beginning breastfeeding
- Termination of the study by the Sponsor
- Loss of ability to freely provide consent through imprisonment or involuntarily incarceration for treatment of either a psychiatric or physical (e.g., infectious disease) illness
- Poor compliance with protocol.
- Discretion of the investigator.
- Disease progression or clinical deterioration that no further benefit from treatment is likely (clinical deterioration should be guided by clinical observation described in Section 6.2 and Investigator's judgment).
- Dosing delays longer than 28 days

All patients who discontinue should comply with protocol specified follow-up procedures as outlined in Section 7.2.5 . The only exception to this requirement is when a patient withdraws consent for all study procedures or loses the ability to consent freely (i.e., is imprisoned or involuntarily incarcerated for the treatment of either a psychiatric or physical illness).

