## **7.5. Records of concomitant medications and procedures**

All medications, including pharmacologic doses of vitamins, herbal medicines, or other alternative medicine all transfusions, including blood component therapies, IV immunoglobulin, and hematopoietic growth factors administered within 28 days before first infusion are to be documented in the appropriate source documents and the CRF, along with the reason for and details of therapy use. Results of assessments must be reviewed by the safety review committee (SRC) before administering the first dose of the next cycle.

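### Section 6.4 lets HLX06 be reduced instead of held for severe or uncontrolled hypertension, with no exception for first-cycle DLTs, which Section 7.2.4.2 bars from re-treatment until recovery

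*Combined protocol and SAP*

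**What the plan says.** **Hypertension guidance (Section 6.4).** Four situations trigger action: systolic pressure above 160 mmHg, diastolic pressure above 100 mmHg, hypertensive crisis, or pressure that antihypertensive treatment does not control. In any of them, "the dose level of HLX06 should be decreased or held until antihypertensive therapy is effectively titrated". The paragraph does not mention DLTs and does not treat crisis differently from the other triggers.

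**DLT definition (synopsis).** First-cycle DLTs include any grade-4 non-hematologic toxicity. They also include "Any grade-3 non-hematologic toxicities lasting more than 3 days despite of optimal supportive care". Hypertension can meet either criterion.

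**Re-treatment after a DLT (synopsis, Dose modification scheme; Sections 3.1.2 and 7.2.4.2).** A patient with a reversible DLT may receive further infusions at the next lower level, "provided that the toxicities have reverted to grade≤1 in 28 days after last infusion". Re-escalation to the level that caused the DLT is not permitted.

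**Neighbouring rules.** For heavy proteinuria, Section 6.4 requires the site to "stop the therapy, and the patients might resume the therapy after proteinuria decreases to" a stated level. For toxicities after cycle 1, Section 6.1 says "Delayed DLTs need to be evaluated on a case-by-case basis".

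**The concern.** Section 6.4 is where a site would look when blood pressure rises. A site that relied on it alone could give a reduced infusion to a patient whose hypertension DLT has not resolved, which the DLT rule does not allow.

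The setting makes this worth correcting. The trial is first-in-human. Section 1.3.1 names grade-3 hypertension as the most common toxicity of ramucirumab alone and expects a similar profile for HLX06. Hypertension is therefore the toxicity for which the two rules are most likely to meet in one patient.

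**Working it through.** The plan states no figure on this point and none has to be reproduced. The check is a comparison of text.

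**Step 1: can both rules apply to the same patient?** Yes. Take a patient in cycle 1 with grade-3 hypertension that persists beyond 3 days despite optimal supportive care. This is a DLT under the synopsis. It also closely matches the Section 6.4 trigger of antihypertensive treatment that fails to control pressure. That hypertension can reach grade 3 is taken from Section 1.3.1; no CTCAE cut-offs from outside the documents are used.

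**Step 2: what does each rule allow before recovery?**

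| Action before grade 1 or lower | Section 6.4 | Section 7.2.4.2 (also synopsis, 3.1.2) |
|---|---|---|
| Infuse at a lower level | Allowed | Not allowed after a DLT |
| Hold | Allowed | Required after a DLT |

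The rules differ only in the first row.

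**Step 3: does the answer depend on how the sentence in Section 6.4 is parsed?** No. If the *until* clause belongs only to holding, reduction carries no recovery condition. If it belongs to both verbs, the reduction still starts before pressure is controlled. It could then also be read as temporary, which fits badly with the ban on re-escalation after a DLT.

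**Step 4: do other provisions settle the next infusion?**
- Sections 6.1 and 10.8 require reporting within 24 hours. That is notification, not approval of the next dose.
- Section 7.2.3 has blood pressure checked at later visits in a cycle ("Vital sign measurements to include temperature, pulse, and blood pressure will be obtained as defined in the Section 14") but gives no pressure at which to withhold. The pre-dose check for new grade 3 or higher abnormalities covers laboratory values.
- The 28-day limit in Sections 7.2.4.1 and 7.2.5 concerns delays. Weekly infusion at a reduced dose involves none.
- Under Section 7.5, results "must be reviewed by the safety review committee (SRC) before administering the first dose of the next cycle". Later infusions within a cycle are not covered.
- Section 7.2.5 requires stopping when the investigator judges that an event "indicates that continued participation in the study is not in the best interest of the patient". This is a judgment, not a rule on recovery.

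These lower the risk, but none of them withdraws the reduction option for a DLT.

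**Step 5: how large is a reduction?** Section 6.4 does not say how many levels; assume one. With the dose levels in Section 3.2, the new dose as a share of the old is:
- 250/500 = 50%
- 500/750 = 67%
- 750/900 = 83%
- 900/1200 = 75%
- 1200/1500 = 80%

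So 50% to 83% of the assigned dose would still be given. At 250 mg there is no lower level and only holding is possible. These shares describe exposure; they do not measure harm.

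**The case against.** The strongest reply is that the two rules can be followed together. Section 6.4 introduces its content as the management of toxicities seen with bevacizumab and ramucirumab, and it offers two options. The DLT rule then restricts one subset. Holding until grade 1 or lower and resuming at the next lower level complies with both. Section 7.2.4.2 is headed as the rule for subsequent infusions and speaks of additional infusions, so it already reaches the weekly doses within a cycle. Sections 7.2 and 7.2.2.1 also send the dose level for the first infusion of a cycle to Section 3, which repeats the recovery condition. The condition is thus stated three times.

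All of this stands. A reader might infer that the plan contradicts itself beyond repair, or leaves the next weekly infusion without any rule. The documents do not support that: a compliant course exists, and Section 7.2.4.2 is best read as governing. What remains is that Section 6.4 makes no exception and does not point to that section.

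The comparison with proteinuria also has limits. That paragraph requires stopping first, but its restart threshold is below 2 g/24 hours and it too says nothing about grade 1 or about DLTs. It shows that Section 6.4 can require a stop, and nothing more.

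Finally, a mandatory hold in hypertensive crisis outside a DLT is a new clinical rule. No conflict between sections requires it, and it is put forward below on that footing.

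**Conclusion.** The point holds as a local inconsistency in a stated safety rule. For hypertension that meets the first-cycle DLT definition, Section 6.4 on its face permits reduced infusions before recovery, and Section 7.2.4.2 does not. It is minor and cheap to correct.

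Its size can be given only in part. Under the one-level assumption, the disputed infusion would be 50% to 83% of the assigned dose. No number of patients can be derived: Section 1.3.1 speaks of grade-3 hypertension with another antibody and gives no rate for hypertension at DLT level. A reader might also infer a fixed maximum number of disputed infusions from weekly dosing and the 28-day window. The documents do not support such a ceiling, because the window runs from the last infusion, which moves forward each time a reduced dose is given.

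DLT counting and MTD selection are unaffected, since the event is already a first-cycle DLT whichever option the site chooses. No conflict is found for hypertension that is not a DLT, for proteinuria, or for delayed DLTs, which are judged case by case. The conclusion rests on reading reduction and holding as true alternatives in Section 6.4.

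**What to change.** Add three sentences to the hypertension paragraph of Section 6.4:

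1. Hypertension that meets first-cycle DLT criteria: hold HLX06 and resume only under Section 7.2.4.2 (grade 1 or lower in 28 days after the last infusion, next lower dose level, no re-escalation).
2. Hypertensive crisis: hold HLX06 until blood pressure is controlled.
3. Dose reduction without a hold applies only to hypertension that is neither a first-cycle DLT nor a hypertensive crisis.

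The first sentence removes the inconsistency. The second is a separate, small safety change, and the third sets the remaining scope of reduction. The proteinuria paragraph and the handling of delayed DLTs stay as they are.

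Design, sample size and visit schedule do not change. The cost is that some patients miss weekly doses they might otherwise have received at a reduced level. For DLTs, Section 7.2.4.2 already requires this; for crisis outside a DLT it is new.

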## **7. STUDY SCHEDULES AND PROCEDURES**

The study of each patient is divided into three periods: screening, treatment and follow-up.

### **7.1. Screening period**

As soon as a patient is considered for this study, and before performing any study procedures, the patient needs to have the nature of the study explained and will be asked to provide a written informed consent. A written, signed and dated, informed consent form (ICF) must be obtained before any study-specific assessments are initiated. A copy of the signed ICF will be given to the patient and a copy will be filed in the medical record. The original version needs to be kept on file with the study records.

Screening assessments must be completed within 28 days prior to the first infusion of the IP (HLX06). Any results falling outside of the reference ranges may be repeated at the discretion of the investigators.

Eligibility criteria for this study have been carefully considered to ensure the safety of the study patients, and to ensure that the study results can be used. It is imperative that patients fully meet all the eligibility criteria. The study population and detailed Inclusion and Exclusion criteria are listed in Section 4 .

Baseline imaging performed as part of the patient's previous routine care before signing the ICF and completed within 42 days before the first infusion of IP can be used as pre-treatment imaging, without the need to repeat the imaging studies.

If there is a question about eligibility and enrollment, the Investigator should consult with the Sponsor's Medical Monitor, or designee, before enrolling into the study.

The screening procedures can be done at inpatient or outpatient setting based on the situation in different site.

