### **4.2. Inclusion criteria**

- Eligible patients must be 18-years of age or older or per local regulations.
- Patients with histologically-proven measurable or evaluable advanced or metastatic solid tumors who have failed standard therapy or for whom no standard therapy is available. (For patients with hepatocellular carcinoma, the diagnosis needs to be supported by dynamic CT/MRI, if pathological confirmation is not attainable)
- Eastern Cooperative Oncology Group (ECOG) performance status of  $\leq 2$  at the time of study entry.
- Able to provide informed consent.
- A life expectancy longer than three months.
- Adequate hematologic functions, as defined by: absolute neutrophil counts  $\geq 1500/\text{mm}^3$ ; a hemoglobin level  $\geq 10 \text{ gm/dL}$ ; a platelet count  $\geq 100,000/\text{mm}^3$ .
- Adequate hepatic function defined by: a total bilirubin level  $\leq 1.5x$  of upper limit of normal (ULN); aspartate transaminase (AST) and alanine transaminase (ALT) levels  $\leq 2.5 \times$  of ULN or  $\leq 5x$  of ULN in known hepatic metastases or with primary hepatocellular carcinoma.
- Adequate renal function, as defined by the creatinine clearance rate  $\geq 50 \text{ mL/minute}$  by Cockcroft-Gault formula.
- Adequate cardiac function defined as left ventricular ejection fraction (LVEF) $\geq 50\%$ .
- Use of effective contraceptive measures if procreative potential exists.
- At least 28 days from prior major surgery, prior cytotoxic chemotherapy, or prior therapy with investigational agents (or medical device) or local radiotherapy before 1st infusion of HLX06.
- For patients with hepatocellular carcinoma, their Child-Pugh score has to be A.
- Able to be followed up as required by the study protocol.
-

The ECOG performance table is listed in Appendix 15. Detailed the Child-Pugh score is listed in Appendix 15.2.

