#### **4.3. Exclusion criteria**

- Patients with large centrally located pulmonary lesions adjacent to or invading large blood vessels.
- Hemoptysis more than  $\frac{1}{2}$  teaspoon (approximately 2-3 mL) of red blood per day.
- Patients who still have  $\geq$  grade 2 toxicities from prior therapies.
- Concurrent unstable or uncontrolled medical conditions with either of the followings:
  - Active systemic infections;
  - Poorly controlled hypertension (systolic blood pressure  $\geq$  160 mmHg or diastolic blood pressure  $\geq$ 100 mmHg), or poor compliance with anti-hypertensive agents;
  - Clinically significant arrhythmia, unstable angina pectoris, congestive heart failure (class III or IV of New York Heart Association [NYHA]) or acute myocardial infarction within 6 months;
  - Uncontrolled diabetes or poor compliance with hypoglycemics;
  - The presence of chronically unhealed wound or ulcers
  - Other chronic diseases, which, in the opinion of the investigator, could compromise safety of the patient or the integrity of study.
- Newly-diagnosed or symptomatic brain metastases (patients with a history of brain metastases must have received definitive surgery or radiotherapy, be clinically stable, and not taking steroids for brain edema). Anticonvulsants are allowed.
- Any concurrent malignancy other than basal cell carcinoma or carcinoma in situ of the cervix. (Patients with a previous malignancy but without evidence of disease for  $\geq$  3 years are allowed to participate).
- Pregnancy (confirmed by serum beta human chorionic gonadotropin [ $\beta$ HCG]) or breast-feeding (for female patients only).
- A known history or clinical evidence of a deep vein or arterial thrombosis, or pulmonary embolism within 6 months of first infusion of HLX06.
- Less than six weeks from last infusion of ramucirumab, or any other anti-VEGF monoclonal antibody therapy (Last treatment with other monoclonal antibodies targeting proteins other than anti-angiogenic factors is permitted if  $\geq$  4 weeks prior to the first infusion of HLX06).

- Proteinuria  $\geq 2+$  in routine urinalysis (patients with a protein value of  $\leq 500$  mg confirmed by a 24-hour urine collection are eligible).
- Known history of human immunodeficiency virus infection (HIV).
- The patient is the investigator, sub-investigator or any one directly involved in the conduct of the study.

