 If all patients should have confirmed pathologic diagnosis, if not, a pathology review might be necessary.

 If no prior record of pathologic diagnosis is available, a tumor biopsy is required.

 PSA is needed for patients with prostate cancer.

 Postmenopausal women must be amenorrheic for at least 12 months in order not to be considered of child-bearing potential.

22. Urinalysis.
23. Chest radiograph (X-ray)
24. 12-lead electrocardiogram (ECG).
25. Tumor imaging with contrasted computerized tomography or MRI (chest, abdomen and pelvis) for tumor assessment (if the imaging studies are less than 6 weeks before 1st infusion of IP, no need to repeat the studies).
26. Contrast brain CT/MRI (if the imaging studies are less than 8 weeks before 1st infusion of HLX06, no need to repeat the test).
27. Cardiac ultrasound or a MUGA scan
28. Bone scan (if signs or symptoms suggestive of bone metastases are present).  
Confirmative X-ray, CT or MRI for bone metastases for patients with positive bone scan. *The selection of imaging modality is based on the discretion of investigators for the benefit of patients.*
29. Concomitant medications including alternative medicines.
30. Assessment of adverse events from prior therapies.

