#### **Documentation of Target and Non-Target Lesions**

All measurable or target lesions, up to a maximum of 5 lesions per organ and 10 lesions total, representative of all sites of disease, will be identified and measured at baseline and followed as target lesions throughout the study. Target lesions should be selected on the basis of their size (longest diameter) and suitability for accurate reproducibility and measurement on follow-up imaging. The SLD for all target lesions will be calculated and reported as the baseline SLD. The baseline SLD will be used as a reference by which to characterize the objective tumor response at each subsequent tumor assessment timepoint. The smallest sum of the longest diameters recorded since baseline will be used as reference when evaluating for progression. All other lesions (or sites of disease) should be identified as non-target lesions and should be recorded at baseline.

Measurement of these lesions is not required, but the presence, absence, or worsening of each should be documented throughout follow-up.

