**Table 7. Definition of lesions and imaging modality and their requirement**

Definitions	Description
Measurable lesions	Target lesions that can be measured accurately in at least one dimension (longest diameter to be recorded) as $\geq 20$ mm with conventional techniques, or as $\geq 10$ mm with spiral (helical) computed tomography (CT) scan or two (2) times the reconstruction interval (RI) when using spiral (helical) or multidetector CT, but not less than 10 mm.
Non-measurable lesions	Non-target lesions not classified as measurable lesions (longest diameter $<20$ mm with conventional techniques or $<10$ mm with spiral CT scan) and truly non-measurable lesions. These include bone lesions on BS, effusions, and leptomeningeal disease. Any measurable lesions that were not classified as target lesions will be classified as non-target lesions.
Target lesions	
All measurable lesions up to a maximum of 5 lesions and 2 lesions per organ, representative of all involved organs, are to be identified as target lesions and recorded and measured. Target lesions are to be selected on the basis of their size (those with the longest diameter) and their suitability for accurate repeated measurements (either by imaging techniques or clinically).
 
All lesions other than target lesions (or sites of disease) are to be identified as nontarget lesions and are to be recorded. Measurements of these lesions are not required, but the presence or absence of each is to be noted.

Definitions	Description
	
Longest diameter for target lesions - The sum of the longest diameter for all target lesions (SLD).
 
Complete response - Disappearance of all target lesions.
 
Partial response: At least a 30% decrease in the sum of the longest diameter of target lesions, taking as reference the Screening sum longest diameter.
 
Stable disease: Neither sufficient shrinkage to qualify for partial response nor sufficient increase to qualify for progressive disease.
 
Progressive disease: At least a 20% increase in the sum of the longest diameters of target lesions (with addition of diameters of any newly emergent measurable lesions), taking as reference the smallest sum of the longest diameters (nadir) recorded since screening.
 
UE/ND/NA

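### A tumour scan up to 42 days old may serve as baseline when prior treatment need end only 28 days before dosing, so the baseline can predate the last treatment

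*Combined protocol and SAP*

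**What the plan says.** Section 7.1 sets a 28-day screening window and then makes an exception for tumour imaging. A routine-care scan obtained before consent and "completed within 42 days before the first infusion of IP can be used as pre-treatment imaging, without the need to repeat the imaging studies". Item 25 of 7.1.1 gives the same waiver for CT or MRI of chest, abdomen and pelvis "if the imaging studies are less than 6 weeks before" the first infusion.

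The interval from earlier treatment is set in 4.2: "At least 28 days from prior major surgery, prior cytotoxic chemotherapy, or prior therapy with investigational agents (or medical device) or local radiotherapy" before the first infusion. Section 4.3 sets a longer interval for one class, excluding patients with "Less than six weeks from last infusion of ramucirumab, or any other anti-VEGF monoclonal antibody therapy". It permits antibodies against other targets from four weeks.

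Section 15.4 makes the baseline sum of longest diameters (SLD) the yardstick: "The baseline SLD will be used as a reference by which to characterize the objective tumor response at each subsequent tumor assessment timepoint". Table 7 defines partial response (PR) as "At least a 30% decrease in the sum of the longest diameter of target lesions, taking as reference the Screening sum longest diameter". Progression is a 20% increase over the smallest sum since screening, so at the first on-treatment scan the baseline sum is the reference for progression too.

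**The concern.** For the treatments named in 4.2, the 28-day screening window and the 28-day treatment-free interval match: a scan inside the window normally follows the last treatment. The 42-day waiver breaks that match. A patient can be scanned, then receive a last chemotherapy cycle or a course of radiotherapy, then wait 28 days and start HLX06, with the scan from before that treatment still serving as baseline.

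Any shrinkage that the earlier treatment produces after the scan is then measured as change from baseline on HLX06. Section 11.3.4 derives ORR (which it calls the primary efficacy parameter), disease control rate, duration of response, PFS and the tumour-burden plots from these measurements. The trial has a single arm, so there is no control group in which the same error would appear and cancel.

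**Working it through.** The plan gives no figure of its own on this point. The check is date arithmetic on its limits, followed by threshold arithmetic on its response criteria.

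**1. Do the two imaging limits agree?** 6 weeks × 7 = 42 days. Section 7.1 includes day 42 and item 25 of 7.1.1 (less than 6 weeks) does not, so they differ only on that day.

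**2. Size of the gap** = oldest accepted scan minus shortest treatment-free interval.
- Surgery, cytotoxic chemotherapy, investigational agents, local radiotherapy (4.2): 42 - 28 = 14 days. Under the strict wording of item 25 it is 41 - 28 = 13 days.
- Antibodies against targets other than angiogenic factors (4.3, four weeks): 42 - 28 = 14 days.
- Ramucirumab and other anti-VEGF antibodies (4.3, six weeks): 42 - 42 = 0 days.

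With the last treatment on day -28, a scan on any of days -42 to -29 (14 days) precedes it. If the scan had to fall inside the 28-day window, that count would be 0.

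**3. Is the gap closed elsewhere?** Sections 4.2, 4.3, 7.1, 7.1.1, 8.3, 11.2.4 and 15.4 contain no rule that the baseline scan must follow the last treatment. Item 5 of 7.1.1 records tumour-specific therapy but does not trigger a repeat scan. The response-evaluable set in 11.2.4 asks for a baseline assessment with measurable disease and says nothing about its timing relative to prior therapy.

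**4. Effect on the thresholds.** Let the baseline sum be S, and let earlier treatment shrink it by a fraction s between the scan and the first infusion, leaving S(1 - s). The values of s are assumptions; the documents give none.
- PR requires a sum of at most 0.7S, so the further on-study shrinkage needed is 1 - 0.7/(1 - s).
- Progression in target lesions at the first on-treatment scan requires 1.2S, so the on-study growth needed to reach it is 1.2/(1 - s) - 1.

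| Assumed s | On-study shrinkage needed for PR | On-study growth needed for progression at first scan |
|---|---|---|
| 0% | 30.0% | 20.0% |
| 10% | 1 - 0.7/0.9 = 22.2% | 1.2/0.9 - 1 = 33.3% |
| 20% | 1 - 0.7/0.8 = 12.5% | 1.2/0.8 - 1 = 50.0% |
| 30% | 1 - 0.7/0.7 = 0.0% | 1.2/0.7 - 1 = 71.4% |

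The middle column bears on ORR, the right-hand column on disease control and PFS.

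**5. Weight of one patient.** One misattributed response moves ORR by 1/30 = 3.3 points if all 30 planned patients have measurable disease, and by 1/10 = 10 points if 10 do.

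**The case against.** Several points on the other side are sound.

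- The waiver is permissive, and the problem needs a chain of events: a scan on days -42 to -29, further treatment ending by day -28, and enough shrinkage afterwards to matter. Patients have failed standard therapy or have none available, which makes a large late response less likely. This limits the frequency. It does not exclude a scan taken before a last cycle or before local radiotherapy.
- Prior-therapy history is collected, so affected patients could be identified at analysis. That is true, but no planned analysis uses the information.
- Responses must be confirmed after at least 28 days (15.4). That gives little protection, because a sum lowered by earlier treatment can stay low.
- The efficacy measures are secondary or descriptive, in at most 30 patients over six dose levels, with no planned test. This stands and limits the importance of the point.

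A reader might also infer more than the documents support.

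- *That the tumour-imaging waiver is the only exception to the 28-day window.* It is not: item 26 of 7.1.1 accepts brain imaging up to 8 weeks old.
- *That a lesion resected after the scan would be scored as a response.* This is implausible. Disease assessment and measurable disease are documented during screening (7.1.1, items 9 and 11), and 15.4 selects target lesions for their suitability for follow-up measurement. The credible case is an irradiated or chemotherapy-treated lesion that is still present.
- *That the waiver's main harm is growth before dosing, with up to 6 + 8 = 14 weeks from baseline to first scan.* The 28-day window already allows 4 + 8 = 12 weeks, so the excess is 2 weeks. Such growth is possible with any scan taken before dosing, whatever the timing of earlier therapy.

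**Conclusion.** The concern holds as a gap in a stated rule. The plan permits a baseline scan up to 14 days older than the last surgery, cytotoxic chemotherapy, investigational agent or local radiotherapy, and nothing requires the reverse order. When that happens and the earlier treatment shrinks the tumour, the bar for PR falls from 30% to 22.2%, 12.5% or 0% on-study shrinkage for an assumed prior effect of 10%, 20% or 30%.

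The documents do not show that this will happen in any given patient, nor how many patients could be affected, so no net bias in ORR can be stated. A reader might infer that the dose-finding result is also at risk. It is not: the MTD in 11.1.1 rests on first-cycle DLTs, and the primary endpoints are adverse events and the MTD. The affected results are ORR, disease control rate, duration of response, PFS and the waterfall plots. The point is secondary in rank, but it should be corrected because the correction is simple and cheap.

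**What to change.** In 7.1 and in item 25 of 7.1.1, accept a routine-care scan as baseline only if it was done after the last prior anticancer treatment, whether systemic therapy, surgery or radiotherapy. Otherwise perform the screening CT/MRI listed in item 25, after that treatment and within the 28-day window. The wording should cover all systemic therapy, because 4.2 and 4.3 name no interval for approved small-molecule agents and the gap for those is not limited to 14 days. The required treatment-free intervals themselves need no change.

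The cost is a sentence in each of two places. A minority of patients lose the waiver and have a scan that the protocol already lists. The change removes the wrong order of scan and treatment. It does not remove growth between scan and first dose: a day -42 scan in a patient whose therapy ended on day -60 would still be accepted.
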